S1 File. The protocol of the study

S2 File. Ethics approval for this study

S3 Table. Sensitivity analysis: effects of individualized, evidence-based counseling on use of antihypertensive drugs when different cutoff values (days) were employed to define the outcome

S4 Table. Sensitivity analyses: effects of individualized, evidence-based counseling on good adherence to treatment when different cutoff values were employed to define the outcome

Title of project: Effects of individualized antihypertensive information on the medication use in hypertensive patients: An exploratory randomized controlled trial.
Principle investigator: [name]

Title:

Effects of individualized antihypertensive information on the medication use in hypertensive patients: An exploratory randomized controlled trial.

Introduction:

In recent years, cardiovascular diseases (CVDs) have become one of the major causes of disease burden in China, accounting for approximately 40% of all deaths.(1, 2) Hypertension is an important modifiable risk factor of CVDs. In a systematic review, antihypertensive therapy has been proven to decrease the risk of stroke and coronary heart disease by 46% and 21%, respectively.(3) The continuous, gradual and smooth increase of absolute CVD risk with blood pressure, makes determining the threshold for initiating antihypertensive therapy a complicated issue. Evidence, people's value and preferences, and resources currently available, are the three major factors taken into account.(4, 5) Given the individualized feature of the other two influencing factors,(6-8) it would be difficult to have a consistent cutoff of CVD risk probability for initiating antihypertensive therapy for every hypertensive patient. Thus, the decision to initiate antihypertensive therapy ought to be based on two-way communication between physicians and patients.(5, 9)

To facilitate shared decision making, patients need to be prepared with knowledge specific to their own disease situations, for instance, absolute risk of CVDs, and benefits and harms of antihypertensive therapy.(10-14) In studies evaluating the efficacy of information communication for patients at risk of CVDs carried out in western countries, patients experienced decreased decisional conflicts,(11-14) had improved knowledge on their disease conditions,(12, 13) and participated more in their decision-making,(10) after obtaining individualized risk information. Moreover, patients were more willing and more compliant to reduce their CVDs risk,(10, 15) compared to their counterparts. Communication on patients' risk information has already been recommended by guidelines in the UK.(4)

However, it remains far less than routine in China, neither recommended by the guideline,(16) nor practiced by physicians.(17) Physician-centered communication and decision making based on their obsolete knowledge still predominates in prescription of antihypertensive therapy and individualized medical information remains far out of patients' reach. (17, 18)

Given the different cultural and social background in China and other foreign countries, it is difficult to predict the benefits of the information communication in the Chinese population. Whether the individualized antihypertensive information will influence patients' medication use in China remains unknown, as is how such information will change patients' medicine-taking behaviors. These are key questions to be answered for potential guideline modifications in the near future. We are going

Title of project: Effects of individualized antihypertensive information on the medication use in hypertensive patients: An exploratory randomized controlled trial.
Principle investigator: [name]

to explore the influence of individualized antihypertensive information on patients' medication use in an exploratory randomized controlled trial.

Aims:

As a primary objective, this study aims to explore the effects of individualized antihypertensive information on medication use (treatment rate and rate of good adherence) in hypertensive patients in China. As a secondary objective, this study aims to assess the roles of this information in the life style and the willingness to take medicines among the hypertensive patients.

Hypothesis:

Our null hypothesis is that the individualized antihypertensive information will have no effects on the rate of treatment or the rate of good adherence in hypertensive patients in China. The alternative hypothesis is that this information will increase both rates.

Methods:

1. Design overview:

A two-site, randomized controlled trial is going to be conducted to compare the individualized antihypertensive information on the basis of life style suggestions and usual care with life style suggestions and usual care solely in hypertensive patients. Eligible patients will be randomly allocated to two paralleled study groups with a ratio of 1:1. Patients will know their groupings, but they will be blind to the hypothesis of this study. Doctors will be blind to patients' grouping status.

2. Settings and patients:

Sequential clinic patients who are eligible and agree to participate will be enrolled in two primary care centers in Longgang District, Shenzhen, Guangdong Province. Inclusion criteria of the study subjects are as follows:

- (1) Patients with primary hypertension;
- (2) Age range: 35-65 years old;
- (3) BP lower than 160/100mmHg at diagnosis, or systolic blood pressure lower than 145mmHg for patients already on antihypertensive medications measured in clinic at recruitment;
- (4) Patients have at least graduated from primary school;
- (5) No deafness, blindness, or dementia, have no difficulty in understanding the antihypertensive information and information in the questionnaire;
- (6) Residents in Shenzhen, patients have no plan to move to other cities or countries in the following 6 months;
- (7) Informed consents have been signed.

Patients with any one of the following conditions will be excluded from this study:

- (1) Patients with hypertensive emergencies and urgencies, which are judged by

Title of project: Effects of individualized antihypertensive information on the medication use in hypertensive patients: An exploratory randomized controlled trial.
 Principle investigator: [name]

-
- physicians in the primary care centers;
- (2) Patients with drug-induced hypertension, drugs include sympathomimetic agents, non-steroidal anti-inflammatory drugs (NSAIDs) and cyclooxygenase 2 (COX-2) inhibitors, corticosteroids, central nervous system (CNS) stimulants, estrogens and progesterone, dietary supplements, serotonin-norepinephrine reuptake inhibitors (SNRIs), immunosuppressants; (19)
 - (3) Patients with histories of coronary heart diseases, cerebrovascular diseases, chronic heart failure, chronic renal diseases, or diabetes mellitus, etc.
 - (4) Patients' risk of cardiovascular diseases over 20% in the future ten years;
 - (5) Patients who did not get total cholesterol (TC) measured within 2 years before the study, or those whose TC values cannot be found in the medical record;
 - (6) Women in pregnancy or lactation;
 - (7) Patients possibly with low compliance to follow-up.

3. Intervention:

Patients in the experimental group will receive individualized antihypertensive information, life style education and care as usual. Patients in the control group only get life style education and usual medical care. The individualized information includes the following contents and an example of intervention with a baseline risk of 20% assumed is attached at the end of this protocol.

- (1) Estimated baseline risk of cardiovascular diseases in the future ten years, estimated by Fuwai equation;

$$P_{men} = 1 - 0.9835 \exp\{0.3277(age_i - 46)/5 + 0.6711(SBP_i - 120)/20 + 0.1367(TC_i - 4.6) + 0.1360(BMI_i - 22)/3 + 0.6894(Smoke_i - 0.73) + 0.1195(Diabetes_i - 0.02)\}$$

$$P_{women} = 1 - 0.9948 \exp\{0.4641(age_i - 45)/5 + 0.6090(SBP_i - 119)/20 + 0.1479(TC_i - 4.6) + 0.1593(BMI_i - 22)/3 + 0.4457(Smoke_i - 0.17) + 0.9946(Diabetes_i - 0.02)\}$$

In patients already on antihypertensive or lipid-lowering medications, treatment effects are adjusted by the following equations:

- a. Antihypertensive medications (20):

BP prior treatment = BP measured + 15mmHg;

- b. Lipid-lowering medications (4):

TC prior treatment

$$= 1.283 * TC \text{ after treatment} - 1.123 + 0.384 * \ln(\text{dose of simvastatin})$$

$$= 1.419 * TC \text{ after treatment} - 2.205 + 0.475 * \ln(\text{dose of atrovastatin})$$

The values of TC measured after the lipid-lowering therapy are going to be obtained from patients' medical record, which were measured within 2 years before the study initiates. Reduction of 26% (3) in baseline risk probabilities by lipid-lowering medications is also taken into consideration in the corresponding

Title of project: Effects of individualized antihypertensive information on the medication use in hypertensive patients: An exploratory randomized controlled trial.
 Principle investigator: [name]

patients.

Since the CVD events estimated by Fuwai equation are mainly the ischemic ones, the estimated probabilities are adjusted based on the ratio of incidences of coronary heart diseases and cerebrovascular diseases (21), as well as that of incidences of ischemic and hemorrhagic cerebrovascular diseases (22) in the Chinese population.

(2) Estimated absolute risk reduction by antihypertensive drug therapy, calculated as follow:

$$\text{Absolute risk reduction (ARR)} = \text{Baseline risk} \times \text{Relative risk reduction (RRR)}$$

RRR: from a systematic review published within 5 years before this study (3);

(3) Medicinal side effects and the estimated probabilities;

(4) Estimated monetary costs of antihypertensive medicines each year;

(5) Qualitative description of opportunistic costs of not initiating pharmaceutical therapy.

4. Outcomes of interest:

* Primary outcomes:

(1) Rate of treatment:

$$\text{Treatment rate} = \frac{\text{Patients currently on antihypertensive medication}}{\text{Total number of patients}} \times 100\%$$

Patients currently on antihypertensive medication are defined as those who took antihypertensive medicines in the past two weeks.

(2) Rate of good adherence:

$$\text{Rate of good adherence} = \frac{\text{Patients with good adherence}}{\text{Total number of patients}} \times 100\%$$

Patients with good adherence are defined as those with percentage of tablets taken as prescribed over 80% in the past week.

* Secondary outcomes:

(1) Changes of willingness to take antihypertensive medicines, obtained at the end of the intervention;

(2) Life style information by self-report, in the past two weeks before the time points of follow-up:

- a. Amount of cigarette smoked per week;
- b. Amount of alcohol consumed per week;
- c. Amount of physical exercises per week in considering of duration and intensity;
- d. Change of amount of salt intake;
- e. Change of amount of fat intake.

5. Implementation of the study:

Title of project: Effects of individualized antihypertensive information on the medication use in hypertensive patients: An exploratory randomized controlled trial.
Principle investigator: [name]

*** Baseline survey and measurement:**

Research assistance will conduct the baseline survey, and extract the values of total cholesterol and prescription information from the medical records. Nurses or doctors will participate to measure the blood pressure, height, and body weight.

(1) Demographic characteristics: gender, age, occupation, education level, medical insurance status;

(2) Life style information: smoking, alcohol drink, salt and fat intake, and physical exercises;

(3) Data used in risk estimation in Fuwai equation: (23)

Systolic blood pressure (SBP): SBPs will be measured at the visit of recruitment. Patients will be asked to rest in sitting position for at least five minutes and avoid drinking coffee, tea, or smoking within thirty minutes before blood pressure taken. Three consecutive blood pressures will be taken with calibrated mercury sphygmomanometer. Record the average SBPs. (23) Doctors or nurses who have been trained to follow the aforementioned standards will take SBPs.

Total cholesterol (TC):

Use the recorded values of TC within in 2 years before the study initiates, taken from medical records.

Smoking status: It is classified as current and non-current smokers. Current smokers are defined as smoking at least one cigarette per day for at least the past 12 months. The definition and classification are consistent with those in the Fuwai Equation. (24-26)

Body mass index (BMI): Weight and height will be measured by the nurses with patients wearing light indoor clothes and no shoes. BMI is calculated as follow:

$$\text{BMI } (\text{kg}/\text{m}^2) = \text{weight } (\text{kg}) / (\text{height } (\text{m}))^2$$

(4) Medication use and prescription information:

Medication use: Record whether patients are currently taking antihypertensive medicines or not. (27) For those on treatment, take detailed information, including doses taken for each time, times of medicine taking per day, days per week in the past week.

Prescription information: Record names of all the prescribed antihypertensive drugs, doses and frequency of medicine taking, as well as doses of lipid-lowering drugs from patients' medical records.

(5) Knowledge and attitudes on hypertension:

- a. The risk probability of CVD in the future 10 years estimated by the patient, whether the patient perceives it as high or low, acceptable risk probability of CVDs in the future 10 years;
- b. Benefits of antihypertensive drugs in reducing the CVD risk probability

Title of project: Effects of individualized antihypertensive information on the medication use in hypertensive patients: An exploratory randomized controlled trial.
Principle investigator: [name]

estimated by the patient, whether the patient perceives it as prominent enough or not;

- c. The perceived severity of CVDs by the patient;
- d. Perceived barriers of taking antihypertensive drugs (adverse effects, costs);
- e. Reasons for taking or not taking antihypertensive drugs.

(6) **Contact information:** home address, at least two telephone numbers to ensure the connection with each patient.

*** Randomization and allocation:**

Random numbers (100 evens and 100 odd numbers) are generated by the software of Stata 10.0. Each random number will be enclosed in an opaque and sealed envelope, and kept in a locked drawer. A specific nurse is centrally in charge of patient allocation in both center and she does not participate in any other parts of the study. Patients will be allocated based on the number they get- evens for the intervention group, and odds for the control group.

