*** Outcomes analyses:**

The two groups will be compared at baseline on demographic features, life style characteristics, knowledge and attitudes to antihypertensive drug therapy, as well as medical use, by *t*-test for continuous variables and chi-square test for binary variables. Regression model for longitudinal data will be applied to examine the effects of intervention on the changes of primary and secondary variables from baseline during follow-up. The software of SPSS 16.0 (SPSS, Inc., Chicago, IL) will be used for baseline comparisons and mixed effects linear model, and Stata 10 for mixed effects logistic model.

References:

1. Ministry of Health. Health Statistics Yearbook 2010. Beijing: Ministry of Health; 2011.

Title of project: Effects of individualized antihypertensive information on the medication use in hypertensive patients: An exploratory randomized controlled trial.
Principle investigator: [name]

-
2. Medscape Website. Global diversity in hypertension: lessons learned. Accessed at <http://www.medscape.com/viewarticle/746194> on May 19, 2013.
 4. NICE Website. Lipid modification: Cardiovascular risk assessment and the modification of blood lipids for the primary and secondary prevention of cardiovascular disease. Accessed at <http://www.nice.org.uk/CG67> on May 10, 2013.
 9. Informed medical decisions foundation Website. What is shared decision making? Accessed at <http://informedmedicaldecisions.org/what-is-shared-decision-making/> on May 12, 2013.

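### Neither the allocation nor the planned models are described as using centre, so a chance difference in centre mix between arms goes uncontrolled; the effect is small and the remedy cheap.

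*Combined protocol and SAP*

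**What the plan says.** Under Settings and patients, eligible patients "will be enrolled in two primary care centers in Longgang District". Under Design overview, "Eligible patients will be randomly allocated to two paralleled study groups with a ratio of 1:1".

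The section Randomization and allocation describes how this is done: "Random numbers (100 evens and 100 odd numbers) are generated by the software of Stata 10.0". The numbers go into sealed opaque envelopes kept in a locked drawer, and "A specific nurse is centrally in charge of patient allocation in both center". Even numbers go to intervention and odd numbers to control. No strata, blocks or separate envelope sets per centre are mentioned.

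Under Outcomes analyses, "Regression model for longitudinal data will be applied to examine the effects of intervention on the changes of primary and secondary variables from baseline". The software sentence adds a mixed effects linear model in SPSS and "Stata 10 for mixed effects logistic model". No covariates or random effects are listed for either model, and centre is not among the variables to be compared at baseline.

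**The concern.** A set of 100 even and 100 odd numbers balances the arms over all 200 patients, but not within a centre. One centre can therefore supply more of the intervention arm than of the control arm.

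Both primary outcomes concern medication use, and adherence is judged against what was prescribed. The Introduction says that physician-centred decisions still dominate antihypertensive prescribing in China. It is therefore plausible, though not shown, that the two centres differ on these outcomes. If they do, part of that difference enters the comparison of arms in the one allocation that is realised. Without a centre term the model cannot remove it.

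The analysts also know the arms (Blinding section). Leaving centre adjustment unspecified therefore leaves a choice that could be made with grouping known.

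**Working it through.** **Inputs from the protocol.** 200 numbers, 100 per arm; two centres; target difference 0.20; control treatment rate 0.75; baseline adherence rate 0.40; α = 0.05; power 0.80; 10% loss to follow-up.

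**Inputs assumed.** 100 patients per centre, and a difference between centres (gap) of 10, 20 or 30 points on the outcome. The protocol gives neither the recruitment split nor any rate by centre.

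**The plan's own figure.** The protocol states no figure on centre balance. Its sample size sets the scale: 2 × (1.960 + 0.842)² × 0.65 × 0.35 / 0.20² = 89.3, so 90 per group, and 90/0.90 = 100. This reproduces the stated numbers with rates of 0.75 and 0.55. The direction of that difference is a separate matter; here only the 20-point target is used.

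**Step 1: how far centre mix can differ.** Under one shared list, the number X of a centre's 100 patients who go to intervention is hypergeometric.
- Variance of X = 100 × 0.5 × 0.5 × (100/199) = 12.56, so SD = 3.54. The 95% range is 43 to 57.
- Difference in centre share between arms, s = (2X − 100)/100. Its SD is 2 × 3.54/100 = 0.071. At X = 57, s = 0.14.
- The probability of a difference of at least 10 points is 0.20.
- With 60, 40 or 20 patients in the smaller centre, the 95% limit is 12, 12 or 8 points.

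**Step 2: shift in a crude follow-up difference** = s × gap.

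| Centre gap | Typical (1 SD) | 95% limit |
|---|---|---|
| 10 points | 0.7 | 1.4 |
| 20 points | 1.4 | 2.8 |
| 30 points | 2.1 | 4.2 |

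For comparison, the standard error of the difference is √(2 × 0.75 × 0.25/100) = 6.1 points at a rate of 0.75 and √(2 × 0.40 × 0.60/100) = 6.9 points at 0.40.

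**Step 3: shift when change is modelled.** Let the gap be d0 at baseline and d1 at follow-up. On the difference scale the shift in the between-arm difference in change is s × (d1 − d0). If the gap is 20 points at both times, the shift is zero. If it widens from 20 to 30 points, the shift is 0.071 × 10 = 0.7 points typically and 0.14 × 10 = 1.4 at the 95% limit. In a logistic model the cancellation is approximate.

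**Step 4: error rate and power of the crude comparison.** 40,000 simulated trials per setting, 100 per arm, gaps of 0 to 30 points:
- No effect, shared list: the unstratified two-proportion test rejects in 0.047 to 0.053 of trials, and the mean estimated difference is zero within simulation error.
- No effect, given a realised 57/43 split: the unstratified test rejects in about 0.05, 0.07 and 0.08 to 0.09 of trials for gaps of 10, 20 and 30 points. The Cochran-Mantel-Haenszel test stratified by centre stays at about 0.05.
- Rates 0.40 and 0.60, shared list: power of the unstratified test is 0.83 throughout. Power of the stratified test is 0.82, 0.82, 0.83 and 0.85 at gaps of 0, 10, 20 and 30 points.

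These simulations concern a crude follow-up comparison, not the planned longitudinal model.

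**The case against.** The strongest reply is that the planned analysis concerns change from baseline. A stable prescribing difference between centres is present at both times and largely cancels, so the crude shifts in Step 2 do not measure harm to that analysis. This stands. What remains is any centre difference in change, for example through doctors' attitudes or contamination during six months, both of which the follow-up interviews ask about. Its size is unknown, and because the model is not fully specified, the degree of protection cannot be confirmed.

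A second reply is that both centres are primary care centres in one district, with common eligibility rules and identically trained educators, and that no centre gap is documented. This also stands: the gaps used here are assumptions.

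Three stronger readings are tempting and are not supported.
- A reader might infer that the estimate is biased or the false-positive rate inflated. Randomisation leaves the estimate unbiased on average and the overall error rate at its nominal level. The raised rates in Step 4 are conditional on a split at the edge of the 95% range.
- A reader might infer that the protocol rules centre out. It does not. One shared list is the natural reading but is not stated in words, and centre is absent from models that list no covariates at all.
- A reader might infer that the trial's actual allocation followed the 100/100 calculation. In S4 Table, 71 is 66.4% of control and 72 is 69.9% of intervention. These imply about 71/0.664 = 107 and 72/0.699 = 103 patients, 210 in all, which is more than the 200 numbers planned.

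**Conclusion.** The point holds as a modest one about design and precision. As written, neither the allocation nor the models use centre, so a chance centre imbalance is not controlled. In a crude comparison the shift would typically be 0.7 to 2.1 points and 1.4 to 4.2 at the 95% limit, against a 20-point target and a standard error of 6 to 7 points. In the planned change-from-baseline analysis it would be smaller. Simulated power improves by at most about 0.02 for gaps up to 30 points. All of this rests on an assumed 100/100 split and assumed gaps. If the centres are alike, there is nothing to gain beyond having the model fixed in advance.

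**What to change.** **Outcomes analyses.** Pre-specify centre as a fixed effect in both the mixed effects logistic and the mixed effects linear models. Where the treatment effect is expressed as change over time, add centre-by-time as well, because a centre main effect alone absorbs only the stable gap that change already removes.

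**Randomization and allocation.** State whether the envelopes were divided by centre. If allocation is still open, generate a separate sequence for each centre in randomly varying blocks, held by the same independent nurse. S3 and S4 Tables report third follow-up results, so for those patients only the model change can be made.

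**Cost.** One or two extra model parameters, a second envelope set and a few spare envelopes because the split between centres is not known in advance. Blocking within centre also makes upcoming assignments somewhat easier to guess, since patients, health educators and interviewers know the arm. Random variation of block size limits this but does not remove it. No extra patients or staff are needed.
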